3.2 Secondary

- To compare ORR of nivolumab to sorafenib. ORR will be determined from assessment by BICR based on RECIST 1.1
- To compare PFS of nivolumab and sorafenib. PFS will be determined from assessments by BICR based on RECIST 1.1
- To evaluate the relationship between tumor PD-L1 expression and efficacy

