7.6.8 Multiple Events

See Core Safety SAP.³³

7.6.9 *Other Events of Special Interest*

See Core Safety SAP. ³³

7.6.10 *Immune-Mediated Adverse Events*

See Core Safety SAP. ³³

7.6.11 *Laboratory Parameters*

See Core Safety SAP. ³³

7.6.12 *Vital Signs*

See Core Safety SAP. ³³

7.6.13 *Immunogenicity Analysis*

See Core Safety SAP. ³³

7.6.14 *Pregnancy*

[figure not shown]
See Core Safety SAP. ³³

7.6.15 *Adverse Events By Subgroup*

See Core Safety SAP. ³³ Region subgroups are formed by US/Canada/Europe vs Asia vs Asia excluding Japan vs. Japan.

7.7 *Pharmacokinetics*

The nivolumab concentration data obtained in this study may be combined with data from other studies in the clinical development program to develop a population PK model. This model may be used to evaluate the effects of intrinsic and extrinsic covariates on the PK of nivolumab. In addition, exposure-response analyses with selected efficacy and safety endpoints may be conducted. Results of population PK and exposure response-analyses will be reported separately.

7.8.1 *PD-L1 Expression*

The definition of PD-L1 expression and PD-L1 status is described in [Section 4.3.3](#). Analyses of PD-L1 expression are descriptive in nature and intended to examine the distribution of PD-L1 expression and assess potential association between PD-L1 expression and efficacy measures. All the analyses will be based on baseline PD-L1 expression.

7.8.1.1 *Analyses of PD-L1*

Analyses of PD-L1 will include:

- 1) Examine the distribution of PD-L1 expression

- 2) Assess potential association between PD-L1 expression and efficacy measures
- 3) Evaluate the potential predictive relationship of the PD-L1 status and efficacy measures

- 1) Descriptive statistics of PD-L1 expression and PD-L1 status

- Listing of all PD-L1 IHC data, all randomized subjects
- Summary of tumor specimen acquisition and characteristics, all randomized subjects
- Summary statistics of PD-L1 expression by treatment group as randomized and overall, all PD-L1 quantifiable subjects
- Frequency of PD-L1 categorization or status ($\geq 1\%$, $< 1\%$), including ‘missing’, ‘indeterminate’ and ‘not evaluable’, by treatment group as randomized and overall, all randomized subjects

- 2) Evaluation of associations between PD-L1 status and efficacy measures

Analyses will be based on all randomized subjects if not otherwise specified. Each analysis will be performed for the subgroups listed below if not otherwise specified.

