- Each PD-L1 status subgroup
- PD-L1 expression missing or indeterminate or not evaluable subgroup

Analyses for OS:

For each of the subgroups:

- OS curves will be estimated using the KM product limit method for each treatment group. Two-sided, 95% confidence intervals for median OS will be computed by Brookmeyer and Crowley method.

Analyses for ORR per BICR RECIST 1.1:

For each of the subgroups:

- Frequency and percentage of BOR will be summarized for each treatment group as randomized.
- ORR will be computed by treatment group as randomized along with exact 95% CIs using the Clopper-Pearson method.
- Odds ratios between the treatments will be provided along with the 95% CI.

For PD-L1 quantifiable subjects, box plots of PD-L1 expression versus response status will be provided by treatment group as randomized.

Receiver Operating Characteristics (ROC) analysis with BOR (CR+PR vs others) will be performed to help assess whether there is a clinically meaningful threshold of PD-L1 expression.

For PD-L1 quantifiable subjects, plots of ROC curve by treatment group as randomized will be provided.

Analyses for PFS per BICR RECIST 1.1:

For each of the subgroups:

- PFS curves will be estimated using the KM product limit method for each treatment group. Two-sided, 95% confidence intervals for median PFS will be computed by Brookmeyer and Crowley method.

3) Evaluation of the potential predictive relationship of PD-L1 status for efficacy measures

Analyses will be based on all PD-L1 quantifiable subjects.

Analyses for OS:

When appropriate, a Cox proportional hazards regression model will be fitted for OS with treatment (treatment groups as randomized), PD-L1 status, and treatment by PD-L1 status interaction. Although the study is not designed to have appropriate power to formally test the interaction of the model, an interaction test at significance level of 0.2 will warrant further exploration and the following statistics will be reported:

- Interaction p-value
- Hazard ratio of treatment vs. control and its associated 95% CI for each of the PD-L1 status subgroup
- Hazard ratio PD-L1 $\geq 1\%$ vs. $< 1\%$ and its associated 95% CI within each treatment group

Analyses for ORR per BICR RECIST 1.1:

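### SAP 7.8.1.1 part 3 can be read as reporting the PD-L1 interaction results only when the interaction test passes 0.2; it should say that they are reported regardless

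*SAP*

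**What the plan says.** SAP 3.2 lists a secondary objective: "To evaluate the relationship between tumor PD-L1 expression and efficacy". SAP 7.8.1 says that "Analyses of PD-L1 expression are descriptive in nature", and 7.8.1.1 sets out three parts.

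- **Part 1** describes the distribution of PD-L1 expression.
- **Part 2** gives results within PD-L1 subgroups, with no significance condition. For OS, "OS curves will be estimated using the KM product limit method for each treatment group", with medians and CIs. For PFS, "PFS curves will be estimated using the KM product limit method for each treatment group", also with medians and CIs. For ORR, rates with exact CIs are given and "Odds ratios between the treatments will be provided along with the 95% CI".
- **Part 3** addresses whether PD-L1 status is predictive. For each of OS, ORR and PFS, a model with treatment, PD-L1 status and their interaction is fitted where appropriate, a condition that is not defined. The SAP concedes the lack of power ("Although the study is not designed to have appropriate power to formally test the interaction of the model") and continues that "an interaction test at significance level of 0.2 will warrant further exploration and the following statistics will be reported". For OS, the list that follows is the interaction p-value, "Hazard ratio of treatment vs. control and its associated 95% CI for each of the PD-L1 status subgroup", and the PD-L1 ≥1% versus <1% hazard ratio within each arm. ORR and PFS have matching lists.

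Outside this section, SAP 7.5.1.4 includes baseline PD-L1 status in the OS forest plot (hazard ratio and 95% CI). A hazard ratio is withheld there only when a category has fewer than 10 subjects in an arm. SAP 7.5.3 says only that PFS might be analysed in some key subgroups.

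**The concern.** A significance level can warrant something only if it is met. The sentence uses the 0.2 test as the subject of both the further exploration and the reporting, so a programmer could reasonably produce the list only when p < 0.2. Another could produce it always. Two faithful implementations of the same SAP would then give different reports.

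Under the conditional reading, the results that speak directly to prediction are selected on their own size. What passes the screen is on average too far from no interaction, and a null interaction result is not printed. The problem is greatest where power is low, which the SAP says is the case here. The results also have a further use: protocol 8.4.2.4 says that a meaningful association would lead to work on PD-L1 as a predictive biomarker, including choice of a cut-off, possibly across studies. Screened estimates would be a poor input to that work.

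**Working it through.** **1. What depends on the screen under the conditional reading**

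| Result by PD-L1 status | Reported without condition? |
|---|---|
| OS treatment hazard ratio | Yes, forest plot (SAP 7.5.1.4) |
| OS curves and medians | Yes, part 2 |
| ORR, treatment odds ratio | Yes, part 2 |
| PFS curves and medians | Yes, part 2 |
| PFS treatment hazard ratio | Not found; 7.5.3 makes no commitment |
| PD-L1 ≥1% vs <1% ratio within arm, all three endpoints | Not found |
| Interaction p-value, all three endpoints | Not found |

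In the interaction model, the difference between the two subgroup log ratios equals the interaction term, and so does the difference between the two within-arm PD-L1 log ratios. Screening on the interaction therefore pushes both pairs apart.

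**2. Effect of the screen on the z scale**

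This needs no assumption about PD-L1 prevalence. Take the test as two-sided (the SAP does not say), so the critical value is 1.2816. With no true interaction:

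- P(reported) = 0.20.
- Mean |z| when reported = 2 × φ(1.2816) / 0.20 = 2 × 0.1755 / 0.20 = 1.75.
- Mean |z| with no screen = √(2/π) = 0.80.
- Ratio = 1.755 / 0.798 = 2.2.

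The selected values are symmetric about zero, so the mean signed log ratio stays at 0. The distortion is in magnitude, not in a fixed direction.

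**3. Background check of the variance formula**

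The documents give no power figure for the interaction. The OS design can be checked with the same approximation, variance of a log hazard ratio = 4/events under 1:1 allocation. With 416 and 520 deaths, HR 0.74 and O'Brien-Fleming-type spending, the nominal levels are 0.0244 and 0.0429 (SAP section 5: 0.024 and 0.043), the critical hazard ratios are 0.802 and 0.837 (0.80 and 0.84), and power is 92.5% (91.5%, by simulation). The approximation is adequate.

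**4. Ratio scale, for illustration**

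Let f be the share of events in PD-L1 ≥1% subjects. The documents do not give it, so 15% to 40% is assumed. Then

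SE(log ratio of hazard ratios) = √(4/(fD) + 4/((1−f)D)),

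and the typical reported magnitude with no true interaction is exp(1.755 × SE) or its reciprocal.

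| D | f | SE | Typical ratio, or reciprocal |
|---|---|---|---|
| 520 (OS deaths, SAP 5) | 0.15 | 0.246 | 1.54 |
| 520 | 0.20 | 0.219 | 1.47 |
| 520 | 0.40 | 0.179 | 1.37 |
| 722 (PFS events, SAP 7.5.4.2) | 0.15 | 0.208 | 1.44 |
| 722 | 0.20 | 0.186 | 1.39 |
| 722 | 0.40 | 0.152 | 1.31 |

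For example, with D = 520 and f = 0.20: √(4/104 + 4/416) = 0.219, and exp(1.755 × 0.219) = 1.47.

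The PFS rows matter more, because the OS subgroup hazard ratios are reported anyway. Both D values assume that every event is in a subject with quantifiable PD-L1. Fewer events would widen the SE and raise the typical ratio.

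**5. A real interaction that is missed**

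For a true ratio of 0.70 (log −0.357), the chance of failing the screen is 1 − [Φ(0.357/SE − 1.2816) + Φ(−0.357/SE − 1.2816)]. On the OS rows, SE 0.179 gives 24% and SE 0.246 gives 43%. On the PFS rows, SE 0.152 gives 14% and SE 0.208 gives 33%.

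**The case against.** The strongest reply is that the sentence contains no conditional word. Where this SAP withholds or conditions output, it says so: the subgroup-size rule in 7.5.1.4, the ORR and PFS p-values in 7.5.2 and 7.5.3, and the 10% disagreement rule in 7.5.1.3. Part 3 can fairly be read as using 0.2 to flag further exploration while the list is reported anyway. This stands as far as showing that the conditional reading is not the only one. It does not remove the ambiguity.

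A reader might infer that the whole PD-L1 objective is reported only when a difference appears. The documents do not support that. Parts 1 and 2 and the forest plot deliver the descriptive analysis that protocol 8.4.2.4 calls for, and more, with no significance condition. From the OS hazard ratios and ORR odds ratios reported there, a reader could work out an approximate interaction for those two endpoints.

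A reader might also take the 1.47 above as an average upward bias in the OS interaction. It is a folded magnitude: 1.47 or its reciprocal, with a mean log ratio of zero. It also concerns an endpoint whose subgroup hazard ratios are not withheld.

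Finally, the analyses are labelled descriptive, and p-values outside the OS, ORR and PFS hierarchy are descriptive too (SAP 7.1). That limits the stakes, but a descriptive result has even less need of a significance screen. Parts of the SAP around the PD-L1 section are blacked out, so the entries marked as not found refer to the visible text.

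**Conclusion.** The point holds as an ambiguity with a limited consequence. On a natural reading, the part-3 sentence makes three sets of results depend on p < 0.2: the interaction p-values for OS, ORR and PFS, the PFS treatment hazard ratios by PD-L1 status, and the within-arm PD-L1 ratios. In that case, with no true interaction, they would appear about one time in five, with an interaction z about 2.2 times its unscreened mean magnitude, in either direction. That figure rests only on a two-sided test and a normal approximation. Every ratio-scale figure also rests on an assumed PD-L1 prevalence and on all events being in PD-L1 quantifiable subjects. On the other reading, nothing is lost. No confirmatory conclusion is touched: the OS type I error and the OS, ORR, PFS hierarchy are unaffected. This is a desirable wording change, not a serious flaw.

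**What to change.** In each of the three part-3 paragraphs (OS, ORR, PFS), replace the sentence with wording such as: The interaction ratio with its 95% CI and p-value, the treatment ratio in each PD-L1 subgroup and the PD-L1 ratio within each arm will be reported regardless of the interaction p-value. If a 0.2 threshold is wanted, add that it serves only to trigger further exploration. State also when a model would not be fitted, in terms that do not depend on the result, such as too few subjects or events in a category.

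The cost is SAP wording; the models are already planned, and the interaction ratio comes from the same fits. SAP version 4.0 (18 May 2020) is later than the database lock of 5 June 2019, so the change should be dated and labelled as a clarification. It adds a commitment to report and removes no analysis.

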7.10 Post Hoc Analyses

This section documents the statistical analyses plan being or to be conducted after the primary database lock for final OS analyses (Database locked on June 05, 2019). For ease of reference in this section, vascular invasion will be referred to as VI; extrahepatic spread will be referred to as EHS; correspondingly, vascular invasion and/or extrahepatic spread will be referred to as VI/EHS.

There are three types of analyses.

- Section 7.10.1 documents planned analyses using the VI/EHS stratification factor determined by BICR (see Independent Radiology Review Charter³²) and efficacy data from the same database lock indicated above. BICR review of baseline scans is planned to be completed and BICR-based VI/EHS stratification factor locked in approximately August 2020. Analysis results will be summarized in a clinical study report (CSR) addendum.
- [Section 7.10.2](#) documents post-hoc sensitivity analyses for the primary endpoint of OS using statistical methods which account for the non-proportionality of the observed OS curves.

Results of all above analyses will be summarized in clinical summary documents to support regulatory filings.

7.10.1 Analyses Based on VI/EHS Status per BICR Assessment

7.10.1.1 *Background of Assessment for the VI/EHS Randomization Stratification Factor*

As background, the stratification factors for this study included HCV vs non-HCV status, VI/EHS (Yes vs No), and Asia vs non-Asia. In the March 2018 DMC routine safety review, BMS received an action item from the DMC that highlighted an observed discrepancy in values between the stratification factors via the IVRS and the CRF. In response to the DMC action item, BMS added a sensitivity analysis in the SAP to conduct a stratified analysis using CRF source if observed discrepancy rate for all stratification factors is at least 10% (see [Section 7.5.1.3](#)). Given that subjects were already randomized into the trial and enrollment was complete, it was not possible to make any changes to the stratification through the IVRS. As such, prior to the database lock on June 05, 2019, BMS conducted data review and queried the sites for all identified discrepancies with IVRS and CRF. After lock, the discrepancy rate between the IVRS and the CRF, was over pre-specified 10% (with 9.3% for VI/EHS stratification factor and 0.8% discrepancy in the HCV stratification factor). The pre-planned sensitivity analysis was therefore triggered as part of the final analyses of OS.

During discussion with the FDA, concerns were raised by the Agency regarding the potential for bias as only discrepant cases were reviewed and the lack of complete justification for changes made in the CRF as a result of the review. Due to this, BMS proposed and planned to perform a formal blinded independent centralized review (BICR) of scans to determine VI/EHS status for all

randomized subjects from the original baseline scan. The planned radiology review was documented in the BICR charter³². This section will describe the analyses to be performed utilizing the VI/EHS status per BICR.

7.10.1.2 Determination of VI/EHS Status per BICR Assessment

According to the BICR charter³², the status of VI and EHS will be adjudicated separately and provided to BMS with three possible outcomes: Yes, no, or unknown (due to situations not evaluable). The overall status of VI/EHS will then be derived by BMS based on the following table with each case of VI status and EHS status for each subject.

Table 7.10.1.2-1: VI/EHS Status per BICR

VI	EHS	VI/EHS
Yes	Yes	Yes
Yes	No	Yes
Yes	Unknown	Yes
No	Yes	Yes
No	No	No
No	Unknown	Unknown
Unknown	Yes	Yes
Unknown	No	Unknown
Unknown	Unknown	Unknown

7.10.1.3 Baseline characteristics

The following baseline disease characteristics will be summarized by treatment group. By-subject listings will also be provided for subject level detail of the BICR assessment.

- VI per BICR (Yes/No/Unknown)
- EHS per BICR (Yes/No/Unknown)
- VI/EHS per BICR (Yes/No/Unknown)

A summary table (cross-tabulation) by treatment group for the stratification factor VI/EHS will be provided to show any discrepancies between what was reported through IVRS and the BICR assessment. A similar summary table will be provided for VI/EHS determined by CRF and by the BICR.

7.10.1.4 Stratified analyses

To conduct stratified analyses based on VI/EHS assessed by BICR, we define the BICR strata as strata determined by the following factors at baseline:

- VI/EHS per BICR

- HCV/non-HCV per IVRS
- Asia/non-Asia per IVRS

Stratified Analyses for OS

The distribution of OS will be compared in two treatment groups via a two-sided stratified log-rank test using the BICR strata. In addition, based on the same strata, a stratified Cox proportional hazards regression model will be used to estimate hazard ratio between treatment groups along with the 95% CI. These are the same stratified analyses as outlined in [Section 7.5.1.1](#) and [Section 7.5.1.2](#) with the VI/EHS stratification factor per IVRS replaced by the one per BICR.

To assess consistency of treatment effects in subsets per different assessments of stratification factors, a forest plot of the OS hazard ratio and 95% CI will be produced for the following variables:

- VI/EHS (Yes/No) per IVRS
- VI/EHS (Yes/No/Unknown) per CRF
- VI/EHS (Yes/No/Unknown) per BICR
- VI (Yes/No) per IVRS
- EHS (Yes/No) per IVRS
- VI (Yes/No/Unknown) per CRF
- EHS (Yes/No/Unknown) per CRF
- VI (Yes/No/Unknown) per BICR
- EHS (Yes/No/Unknown) per BICR

If a subgroup category has less than 10 subjects in a treatment group, then HR will not be reported for that subgroup.

Stratified analysis for ORR and PFS per BICR RECIST 1.1

Based on the BICR strata, the following stratified analyses are planned for the ORR and PFS assessed by BICR per RECIST 1.1.

ORR will be compared between two treatment groups using a stratified two-sided CMH test. The stratified odds ratios (Mantel-Haenszel estimator) between the treatments will be calculated along with the 95% CI. An estimate of the differences in ORRs and corresponding 95% CI will be calculated based on CMH method of weighting, stratified by the BICR strata. These are the same stratified analyses as outlined in [Section 7.5.2](#), with the VI/EHS stratification factor per IVRS replaced by the one per BICR.

PFS will be compared between the two treatment groups via the stratified log-rank test. A stratified Cox proportional hazards regression model will be used to estimate HR and 95% CI. These are the same stratified analyses as outlined in [Section 7.5.3](#), with the VI/EHS stratification factor per IVRS replaced by the one per BICR.

[figure not shown]
7.10.2 Analyses for Investigating Non-Proportionality in OS Curves

7.10.2.1 Piecewise hazard ratio

Having examined the OS KM curves in the final analyses, we observed that the HR does not appear to be constant over time: the OS in nivolumab demonstrated similar benefit to sorafenib, with two curves overlapping with each other in the first 8 months; afterwards, the two curves started to separate, with clear separation towards the tails. Therefore, piecewise HRs and 95% CI will be calculated for the time periods of the first 8 months and the subsequent period later than the first 8 months. The HRs and 95% CI will be estimated based on stratified Cox models with a time-dependent-covariate approach. The stratified analyses will be repeated for the three assessments of stratification factors: the stratification factors per IVRS, the ones per CRF, and the BICR strata.

7.10.2.2 Max-Combo test

Since the OS curves indicate the HR is not constant over time with the clear delayed separation, the power of the standard logrank test is reduced. In this case, as suggested by the non-proportional hazards working group, the Max-Combo test is a promising approach with the flexibility of allowing different types of non-proportionality and robustness under model mis-specification³⁷. The working group also provided the R package nphsim to facilitate such testing procedures. We will apply the Max-Combo test to the OS data with the following parameter setting (rho, gamma) of Fleming-Harrington class of weights: (rho = 0, gamma = 0) attributes equal weights to all; (rho = 1, gamma = 0) emphasizes early difference in survival curves; (rho = 0, gamma = 1) weight more for late difference; (rho = 1, gamma = 1) emphasizes middle difference. In the current implementation of the R package nphsim, stratification is not available. Therefore, the unstratified Max-Combo test in the package will be applied and the resulting p-value will be reported, along with estimated HR and adjusted 95% CI. Since the stratification is not involved, the results of this sensitivity analysis should only be compared with the original results of the unstratified analysis (see [Section 7.5.1.3](#)).

8 CONVENTIONS

8.1 Date Imputation

The following conventions may be used for imputing partial dates for analyses requiring dates:

- For missing and partial adverse event onset dates, imputation will be performed using the Adverse Event Domain Requirements Specification³⁸.
- Missing and partial Non-Study Medication Domain dates will be imputed using the derivation algorithm described in 4.3.3 of BMS Non-Study Medication Domain Requirements Specification³⁹.
- For death dates, the following conventions will be used for imputing partial dates:
 - If only the day of the month is missing, the 1st of the month will be used to replace the missing day. The imputed date will be compared to the last known date alive day and the maximum will be considered as the death date.
 - If the month or the year is missing, the death date will be imputed as the last known date alive day
 - If the date is completely missing but the reason for death is present the death date will be imputed as the last known date alive day
- For date of progression, the following conventions will be used for imputing partial dates:
 - If only the day of the month is missing, the 1st of the month will be used to replace the missing day. In cases where the date of death is present and complete, the imputed progression date will be compared to the date of death. The minimum of the imputed progression date and date of death will be considered as the date of progression.
 - If the day and month are missing or a date is completely missing, it will be considered as missing.
- For other partial/missing dates, the following conventions may be used:
 - If only the day of the month is missing, the 15th of the month will be used to replace the missing day.
 - If both the day and the month are missing, “July 1” will be used to replace the missing information.
 - If a date is completely missing, it will be considered as missing.

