#### **3.6.1 Withdrawal of Consent**

Subjects who request to discontinue study drug will remain in the study and must continue to be followed for protocol specified follow-up procedures. The only exception to this is when a subject specifically withdraws consent for any further contact with him/her or persons previously authorized by subject to provide this information. Subjects should notify the investigator of the decision to withdraw consent from future follow-up **in writing**, whenever possible. The withdrawal of consent should be explained in detail in the medical records by the investigator, as to whether the withdrawal is from further treatment with study drug only or also from study procedures and/or post treatment study follow-up, and entered on the appropriate CRF page. In the event that vital status (whether the subject is alive or dead) is being measured, publicly available information should be used to determine vital status only as appropriately directed in accordance with local law.

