#### **3.6.2 Lost to Follow-Up**

All reasonable efforts must be made to locate subjects to determine and report their ongoing status. This includes follow-up with persons authorized by the subject as noted above. Lost to follow-up is defined by the inability to reach the subject after a minimum of three documented phone calls, faxes, or emails as well as lack of response by subject to one registered mail letter. All attempts should be documented in the subject's medical records. If it is determined that the subject has died, the site will use permissible local methods to obtain the date and cause of death.

If investigator's use of third-party representative to assist in the follow-up portion of the study has been included in the subject's informed consent, then the investigator may use a Sponsor-retained third-party representative to assist site staff with obtaining subject's contact information or other public vital status data necessary to complete the follow-up portion of the study. The site staff and representative will consult publicly available sources, such as public health registries and databases, in order to obtain updated contact information. If after all attempts, the subject remains

lost to follow-up, then the last known alive date as determined by the investigator should be reported and documented in the subject's medical records.

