4.2 Primary endpoint OS

OS is the primary endpoint for this study. It is defined as the time from the date of randomization to the date of death due to any cause in all randomized subjects. Subjects who are alive will be censored at the last known alive dates.

On treatment visits will occur at Day 1 and every 2 weeks thereafter. Subjects will be treated until unacceptable toxicity or disease progression. Following discontinuation of therapy, safety will be assessed through post-treatment Follow Up visit 2 (~ 100 days from last dose). Survival status will be assessed every 3 months after follow up visits are completed, and may be completed via telephone or in person visits. Note after discontinuation of therapy, tumor imaging assessment will continue until disease progression (see schedule of tumor imaging assessment in [Section 4.1.1](#)).

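### SAP 8.1 drops a known year of death when the month is missing, so an OS event can be dated in a year the record rules out; the effect is probably very small

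*SAP*

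**What the plan says.** SAP 8.1 (Date Imputation) has three rules for incomplete death dates.

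- Only the day missing: the 1st of the recorded month is substituted, and then "The imputed date will be compared to the last known date alive day and the maximum will be considered as the death date".
- Month or year missing: "If the month or the year is missing, the death date will be imputed as the last known date alive day".
- Date wholly missing but a reason for death present: the last known alive date is used.

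For dates with no rule of their own, the same section keeps the year. "If both the day and the month are missing", 1 July is substituted.

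SAP 4.2 gives the definition of OS: "It is defined as the time from the date of randomization to the date of death due to any cause in all randomized subjects". SAP 4.1.2 uses the date of death as the PFS event date when a subject dies without progression and without subsequent anti-cancer therapy. On contact frequency, SAP 4.2 says: "Survival status will be assessed every 3 months after follow up visits are completed".

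Two protocol sections deal with subjects who drop out of contact. If a lost subject is found to have died, Protocol 3.6.2 says "the site will use permissible local methods to obtain the date and cause of death". Where consent has been withdrawn, Protocol 3.6.1 says "publicly available information should be used to determine vital status only as appropriately directed in accordance with local law".

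**The concern.** The second rule applies when either the month or the year is missing, so it covers a death known to have occurred in, say, 2018 with no month. The recorded year is not used, and there is no comparison with 1 January of that year. If the last contact was in 2017 or earlier, the analysis places the death before the year in which the record says it happened. Nothing elsewhere in the SAP or protocol restores the year.

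The date at issue is the event date of the primary endpoint, and it is imputed from less of the recorded information than the section uses for miscellaneous dates. When the rule crosses a year boundary, the error always shortens survival. The trial is open-label, so late tracing could differ between arms, in which case the error would not cancel. The subjects most exposed are those lost or withdrawn and traced later, because their last contact can be old.

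**Working it through.** The plan states no figure to reproduce. The check applies the rule as written and compares it with a version that keeps the known year.

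**Rules compared, for a known year Y and a missing month**

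- SAP 8.1: death date = last known alive date (LKA).
- Year kept: death date = max(1 January Y, LKA).
- Avoidable error = max(0, 1 January Y − LKA).

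**Illustrative dates.** These are invented: death recorded as 2018, randomization 26 Sep 2016. Months = (days + 1)/30.4375, as in SAP 8.2.

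| LKA | OS, SAP rule | OS, year kept | Difference |
|---|---|---|---|
| 2 Oct 2017 | 372/30.4375 = 12.22 | 463/30.4375 = 15.21 | 91 days |
| 15 Nov 2017 | 416/30.4375 = 13.67 | 15.21 | 47 days |
| 10 Feb 2018 | 16.53 | 16.53 | 0 |

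A subject lost early shows the larger case. With LKA 10 Nov 2016 and death recorded as 2018, the avoidable error is 365 days to 10 Nov 2017 plus 52 days to 1 Jan 2018, which is 417 days.

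**How often the boundary is crossed.** Assume deaths are spread evenly over the year and the gap from last contact to death is uniform on 0 to g days. Then:

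- share of year-only deaths that cross = (g/2)/365.25
- mean shortfall to 1 January among those that cross = g/3

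| Maximum gap g | Share crossing | Mean shortfall |
|---|---|---|
| 14 days | 7/365.25 = 1.9% | 4.7 days |
| 91 days (3-monthly contact) | 45.5/365.25 = 12.5% | 30.3 days |
| 182 days | 91/365.25 = 24.9% | 60.7 days |

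Simulation of one million deaths per row agrees (1.9%, 12.5% and 24.9%; 4.7, 30.3 and 60.6 days).

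**Effect on the hazard ratio, on-schedule contact.** 300 trials were simulated with 726 subjects, 39% HCV, sorafenib medians of 10 and 14 months, HR 0.74, uniform accrual over 13 months and cut-off at the 520th death. An assumed 1% to 5% of deaths were moved back by 0 to 3 months. The whole gap was moved without stopping at 1 January, so this exceeds the avoidable error.

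- Both arms affected: mean HR factor 1.000 at 1%, 2% and 5%.
- Nivolumab only: 1.001, 1.002 and 1.004.

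**Effect on the hazard ratio, deliberately severe.** 600 trials per scenario were simulated with SAP Table 5-1 accrual, cut-off at month 33 and true HR near 0.85. Every affected death was moved back 9 months.

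- 2% of sorafenib and 0% of nivolumab deaths: HR 0.848 to 0.841.
- 5% and 1%: HR 0.848 to 0.836, so ln(0.836/0.848) = −0.014. Against a standard error of about 2/√520 = 0.088, this is 0.16 standard errors.
- Equal 2% in both arms: HR 0.849, essentially unchanged.
- Reversed imbalance: HR 0.855 (0% and 2%) and 0.861 (1% and 5%), so the shift can go either way.

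**The case against.** The strongest reply is that this is an edge case with no demonstrated consequence. The event is still counted and only its time moves. The protocol tries to keep such dates rare: sites must seek the date of death, registries and third-party tracing are allowed (3.6.2), and the sponsor can request extra survival contacts (3.6). Neither 3.6.1 nor 3.6.2 says that tracing yields only a year. Most of this stands, and it sets the weight of the point. It does not remove the inconsistency, because the rule gives a wrong date for any year-only death whose last contact was in an earlier year.

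It could also be said that the section opens permissively: "The following conventions may be used for imputing partial dates for analyses requiring dates". That does not help, because the line introducing the death-date rules makes them mandatory.

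Two stronger readings are tempting, and the documents support neither.

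- A reader might charge the whole delay to the true death against the rule. In the 2018 example that is up to 417 + 364 = 781 days. But flooring at 1 January recovers only the 417 days. The other 0 to 364 days remain under the corrected rule too, and choosing the earliest possible date is also what the SAP does when only the day is missing.
- A reader might infer that the rule could carry OS across the projected final significance limit, an observed HR of 0.84 (SAP 5). That takes something like the 5% and 1% scenario with a flat 9-month shift. The documents give no count of year-only deaths, no loss rate and no imbalance between arms, and 9 months is far longer than the gap under 3-monthly contact.

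**Conclusion.** The rule is wrong as written. It discards a recorded year of death and can date the primary-endpoint event in a year the record rules out, contrary to the logic of the day-only rule beside it. This conclusion rests on the text alone.

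The avoidable error per affected subject runs from last contact to 1 January of the recorded year. With on-schedule contact it is zero for roughly seven in eight year-only deaths, averages about 30 days for the rest, and does not exceed about 91 days. It is longer only for lost or withdrawn subjects traced late.

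The effect on the HR cannot be fixed from the documents, because the number of year-only death dates is not given and may be zero. For assumed shares of 1% to 5% and gaps of up to 3 months, the mean HR changes by a factor of 1.000 to 1.004. A material shift would need such deaths to be numerous, long out of contact and unbalanced between arms, which nothing in the documents indicates. Severity: minor.

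**What to change.** Replace the second death-date rule in SAP 8.1 with:

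*If the year is known and the month is missing, the death date is the later of 1 January of that year and the last known alive date. The last known alive date is used alone only when the year is missing.*

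Timing limits how this should be applied. SAP 7.10 records that the database for the final OS analysis was locked on June 05, 2019, and SAP 7.10.2.1 shows that the OS curves have been examined. Substituting a new derivation into the primary analysis now would be a change made with knowledge of the results. The primary OS result should therefore stand under the existing rule, with two additions:

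- Report the number of year-only death dates by arm, with the interval from last contact to 1 January of the recorded year.
- If there are any, rerun OS and PFS under the corrected rule as a sensitivity analysis labelled post hoc. If there are none, a one-line statement closes the point.

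The cost is one sentence in the SAP, one count by arm and, at most, one rerun of two existing derivations. No new data are needed.
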